### 9.3 POPULATIONS FOR ANALYSES

Our analysis will adhere strictly to the intent-to-treat principle. All participants randomized will be analyzed according to their allocation.

**Missing Outcomes:** We distinguish two kinds of missing data: missing data in covariates, and missing data for outcomes. For the latter, we distinguish simple loss to follow-up (as when a patient has needed to move out of the area) from data missing because of the occurrence of a medical event (such as the loss of an eye). We will always report the results of complete case analysis, although such results are known to be biased. In the event of missing baseline covariates among >10% of patients, we will use regression based multiple imputation (with at least 100 replicates) to impute these missing covariates (based only on other variables available at baseline). To compare with the complete case analysis, we will also report multiple-imputation based analysis for missing outcomes (or equivalently, likelihood methods which integrate over the missing outcome data based on the same assumption of missingness at random); such analyses are important to report because of the intent to treat principle. Finally, we conduct sensitivity analyses in which the data are not assumed missing at random, to assess how extreme the missing values would need to be to change the conclusions of the study. We propose use of the R package mice (Multiple Imputation by Chained Equations) for multiple imputation; other choices are available and would serve equally well.

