6.3. Missing data

If outcome data are missing for >15% of participants we will report results from sensitivity analyses for missing data [4,5]. We selected 15% missing because trials with >20% missing values are thought to be a concern for bias [6]. The primary analysis will assume outcomes are

missing completely at random. We will relax this assumption slightly, assuming that outcomes are missing at random (MAR) with an inverse-probability weighted (IPW) estimator. We will model the probability of censoring as a function of baseline patient characteristics with a logistic regression model, and will use the inverse of the predicted probabilities from the model to re-weight the analysis population to reflect the full study population at the time of enrollment, using a doubly-robust targeted maximum likelihood estimator that also includes an outcome model using the same covariates [7]. Baseline characteristics used in the censoring model will include treatment arm, site, age, sex, occupation, medication use at enrollment, eye trauma, ocular measures at enrollment (infiltrate and/or scar size, depth, epithelial defect size, duration of symptoms, BSCVA). We will additionally consider a range of scenarios assuming the outcomes are missing not at random (MNAR), *i.e.* systematically, using a pattern mixture model approach described by Little et al. [4], whereby we model BSCVA with a linear model as a function of covariates listed for the IPW estimator; missing outcomes will then be imputed using the model fit to predict, adding a shift parameter, Δ , that we vary across a range of values.

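### Protocol 9.3 classes a lost eye as missing outcome data, and neither the protocol nor the REAGIR SAP scores it as the known worst outcome that it is

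*Protocol*

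**What the plan says.** Protocol 9.3 divides missing outcomes into ordinary loss to follow-up and "data missing because of the occurrence of a medical event (such as the loss of an eye"). Three steps follow, none of them specific to either kind:

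- Complete case: "We will always report the results of complete case analysis, although such results are known to be biased".
- MAR: "we will also report multiple-imputation based analysis for missing outcomes". A likelihood approach is accepted in place of imputation, and the protocol describes it as "likelihood methods which integrate over the missing outcome data based on the same assumption of missingness at random".
- Non-MAR: "Finally, we conduct sensitivity analyses in which the data are not assumed missing at random". No missingness threshold is attached.

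The same section commits to analysing every randomised participant in the assigned group.

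The REAGIR SAP, section 6.3, makes MCAR the primary assumption, in the sentence that opens "The primary analysis will assume outcomes are". Further work depends on a threshold: "If outcome data are missing for >15% of participants we will report results from sensitivity analyses for missing data". That work is an analysis "assuming that outcomes are missing at random (MAR) with an inverse-probability weighted (IPW) estimator", made doubly robust by targeted maximum likelihood (TMLE), and a pattern-mixture analysis that adds a shift to imputed values. The shift applies to missing outcomes in general, and its range is not given.

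A separate rule covers perforation and therapeutic keratoplasty (TPK). Protocol 9.4.1 carries the last observation forward in the primary analysis. SAP 6.2 uses the actual 6-month acuity and keeps the carried-forward value for sensitivity. Neither says what is entered when the eye has been lost. Protocol 8.1 refers to the manual of operations for the acuity procedure, and the manual is not in the file.

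**The concern.** When an eye is lost, the 6-month visual result is known: that eye has no vision. Calling it missing hands it to methods built for unknown values. Complete-case analysis under MCAR leaves it out. MAR imputation, weighting or TMLE represents it by eyes that still see and have similar baseline data. Either way the worst results drop out of the contrast. If one arm loses more eyes, that arm looks better than it is. Leaving these participants out also sits badly with the commitment to analyse everyone randomised.

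The risk of imbalance is not far-fetched. Protocol 2.2 reports perforation or TPK in about half the patients of one fungal keratitis trial, and an earlier cross-linking trial in deep fungal ulcers that stopped over concern about perforation. These are not eye-loss rates, but they show that a treatment effect on catastrophic outcomes is a live question here.

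**Working it through.** **1. The plan's own figure.** Inputs are from SAP 3.3: SD 0.293, correlation 0.216, 165 per arm, 15% loss, two-sided alpha 0.05.

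- Residual SD = 0.293 × √(1 − 0.216²) = 0.286.
- Evaluable per arm = 165 × 0.85 = 140.25.
- Detectable difference = 0.286 × √(2/140.25) × (1.960 + 1.282) = 0.1107 at 90% power (stated 0.11), and 0.0957 at 80% (stated 0.10).

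The figure reproduces and is not in dispute. It is the yardstick for what follows.

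**2. Where a lost eye goes under the text.**

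| Case | Protocol | REAGIR SAP |
|---|---|---|
| Lost, no earlier perforation/TPK | Complete case; MAR; non-MAR sensitivity | If treated as missing: MCAR in the primary analysis; IPW/TMLE and shift only above 15% missing |
| Lost after perforation/TPK | Last acuity carried forward | Actual 6-month acuity, which is undefined for an absent eye |

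No cell scores the eye as a worst outcome. The SAP trigger is 0.15 × 330 = 49.5, so up to 49 missing outcomes require no sensitivity analysis.

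**3. Size of the shift.** Shift = (difference between arms in the share of eyes lost) × (logMAR gap between a scored lost eye and the mean of sighted eyes). The documents give neither input, so both are assumptions.

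- Low end: 0.005 × 1.0 = 0.005 logMAR; 0.005/0.11 = 5%.
- High end: 0.03 × 2.5 = 0.075 logMAR; 0.075/0.11 = 68%.
- Equal loss and equal gap: 0.
- Per excess eye in an arm of 165: 1.0/165 = 0.006 to 2.5/165 = 0.015 logMAR.
- Excess eyes needed to equal 0.11 (0.11 × 165/gap): about 18 at a gap of 1.0, 12 at 1.5 and 7 at 2.5.

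**4. Simulation check.** There were 2,000 runs with 165 per arm, 15% random loss to follow-up, 4% against 1% of eyes lost, and no treatment effect in sighted eyes. Complete-case analysis and MAR imputation both gave a difference of 0.00. Scoring lost eyes gave about 0.03, 0.05 and 0.09 logMAR at gaps of 1.0, 1.5 and 2.5, against the arm losing more. These slightly exceed 0.03 × gap because every lost eye was kept while 15% of the others were not. The analysed shares are 0.04/(0.04 + 0.96 × 0.85) = 4.67% and 0.01/(0.01 + 0.99 × 0.85) = 1.17%, a difference of 3.50 points.

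**5. Cost of a worst score in the linear model.** With a share p lost in each arm and gap g, SD = √((1 − p) × 0.286² + p(1 − p)g²), and the effect is 0.11 × (1 − p). Power with no lost eyes, at 140.25 per arm, is 0.896. With p = 1%:

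| Gap | SD | Power |
|---|---|---|
| 1.0 | 0.301 | 0.857 |
| 1.5 | 0.321 | 0.810 |
| 2.5 | 0.378 | 0.675 |

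**The case against.** The best defence is that the plan does not stop at MCAR and MAR. Protocol 9.3 asks how extreme the missing values would have to be to overturn the conclusion, and SAP 6.3 adds a shift analysis. A reader might infer that lost eyes are only ever dropped or filled in under MAR; the text does not support that. These analyses are still a partial remedy. The SAP version runs only above 15% missing, gives lost eyes and participants who moved away one shift of unstated range, and leaves the primary result unchanged.

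Some lost eyes are also caught by the perforation/TPK rule. Under the protocol these get a carried-forward value, so they are neither dropped nor imputed, although that value credits them with earlier vision.

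Four other strong readings go too far:

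- That the plan forbids a worst score. It draws a distinction and gives no separate rule; the SAP never mentions a lost eye.
- That MCAR governs all three trials. It is stated only in the REAGIR SAP; the SCUT II and REAGIR II SAPs are not in the file. That SAP's MAR method is weighting with TMLE; multiple imputation is the protocol's.
- That an eye with no light perception is also treated as missing. Protocol 9.3 names only loss of an eye, and the manual may hold a code.
- That the primary contrast is certain to be biased. Bias needs unequal loss.

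The case against a worst score as the sole primary analysis also has force. One chosen value can dominate a linear model, and the power loss in step 5 is material.

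**Conclusion.** The point stands in this form: a known worst outcome is labelled missing, the distinction from ordinary loss to follow-up is drawn and never used, and no rule in either document scores the eye. Followed as written, a lost eye outside the perforation/TPK rule is dropped from a complete-case result or represented by sighted eyes.

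The size is conditional. A shift of 0.005 to 0.075 logMAR (5% to 68% of 0.11) rests wholly on the assumed imbalance of 0.5 to 3 points and gap of 1.0 to 2.5 logMAR, and is zero if the arms lose eyes equally. Eye loss alone would need an excess of about 7 to 18 eyes in one arm to match the design effect. The rule should be fixed in advance, because one chosen after unmasking could look outcome-driven. The documents do not show that the result will be wrong.

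**What to change.** Before unmasking, amend Protocol 9.3 and SAP 6.2 and 6.3 as follows:

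- State that a lost eye is an observed 6-month outcome, not a missing one.
- Restrict MAR imputation or likelihood, weighting and TMLE to true loss to follow-up.
- Always report, whatever the percentage missing, an analysis with lost eyes at a pre-specified worst logMAR value and a rank-based analysis with lost eyes ranked worst.
- Report the number of lost eyes by arm.
- Reconcile Protocol 9.3 and 9.4.1 with SAP 6.2 and 6.3. Say which rule governs an eye lost after perforation or TPK, and whether sensitivity analyses depend on the 15% threshold.

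Take the worst value from the acuity procedure in the manual if it has one; otherwise fix it in the SAP.

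The cost is document changes and two further analyses. A worst score raises the variance: at 1% lost per arm, the SD goes from 0.286 to between 0.301 and 0.378. The rank-based analysis is therefore needed beside it, so that the chosen value does not drive the result. Whether the worst score also enters the primary analysis is the sponsor's choice of estimand, to be made with that power loss in view.

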## 5.4 SCREEN FAILURES

Screen failures are defined as participants who consent to participate in the clinical trial but are not subsequently randomly assigned to the study intervention or entered in the study. A minimal set of screen failure information is required to ensure transparent reporting of screen failure participants, to meet the Consolidated Standards of Reporting Trials (CONSORT) publishing requirements and to respond to queries from regulatory authorities. Minimal information includes demography, screen failure details, eligibility criteria, and any serious adverse event (SAE). In this study, all patients who are enrolled will be randomized and included in the primary analysis, regardless of whether or not they actually receive the assigned intervention.

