## 9.4 STATISTICAL ANALYSES

### 9.4.1 ANALYSIS OF THE PRIMARY EFFICACY ENDPOINT

The **Statistical Analysis Plans** for SCUT II, REAGIR, and REAGIR II include more detail about planned analyses. The primary outcome will be 6-month BSCVA, and the primary analysis of each trial will use the same approach. We will use multiple linear regression models to evaluate BSCVA measured at 6 months with covariates for treatment arm (expressed as a binary indicator variable for steroids and a binary indicator variable for cross-linking), indicators for study site (randomization strata), and BSCVA measured on Day 1 (before treatment). We propose a two-sided alpha of 0.025 for each pairwise primary comparison. Specifically, we propose to contrast Groups 1 and 2 using a linear model in which we use baseline visual acuity and a binary indicator for assignment to Group 2 as predictors, and BSCVA as the outcome variable. We then propose to contrast Groups 2 and 3 separately using a model with baseline visual acuity and a binary indicator for assignment to Group 3 as predictors, with BSCVA as the outcome variable.

For study participants who experience perforation or the need for TPK this will be noted and BSCVA will be recorded prior to performing surgery (either corneal glue or TPK). The last observation (at 3 weeks or 3 months) will be carried forward (LOCF) as the 6-month BSCVA, but a separate secondary analysis will include these study participants actual 6-month visual acuity.

A supplementary analysis using linear mixed effects regression will be conducted to analyze all BSCVA data (including 3-week and 3-month observations). The model will include baseline BSCVA and treatment assignment as covariates (fixed effects) plus a random effect for patient to allow for repeated measures over time. Such analyses will be sharply distinguished from the primary pre-specified analysis. Permutation testing will be the basis of inference. Specifically, we will conduct 10,000 random permutations of treatment assignment, and conduct the primary regression analysis on these re-

randomized data sets. We will then compare the observed regression coefficients to the randomization distribution, reporting the quantiles.

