Visual Acuity at 3 weeks, 3 months, and 12 months. We will compare BSCVA between arms at 3 weeks, 3 months, and 12 months follow-up using the same approach as the primary analysis. We will only complete this analysis after the primary analysis is complete and the trial is unmasked.

Scar/infiltrate. The analysis for scar/infiltrate size will follow the templates for visual acuity given

above. Multiple linear regression models will be used to evaluate 3-week, 3-month, 6-month, and 12-month scar size by treatment arm while correcting for baseline measurements. Corneal thinning and scarring will be evaluated similarly using Anterior Segment Optical Coherence Tomography (AS-OCT) correcting for baseline values.

Corneal Perforation. A Cox proportional hazards model will estimate the hazard of perforation, defined as perforation (flat anterior chamber with presence of iris plugging a defect in the cornea or seidel positivity) or the need for TPK while correcting for baseline infiltrate depth.

Microbiological cure. We will re-culture all study participants at Day 2, prior to starting antibiotics to assess the effect of RB-PDT on rate of microbiological cure. We hypothesize that those in the RB-PDT group (Arm 2) will have a higher rate of microbiological cure on 2 day cultures than those randomized to the Sham group (Arm 1).

We propose the primary analysis to be a Fisher's exact test comparing the proportion of positivity at follow-up between initially culture positive individuals who were assigned to RB-PDT (Arm 1) versus initially culture positive individuals assigned to the Sham group (Arm 1).

Additionally, we will report the results for initially culture negative individuals as a supplementary analysis in a linear binomial regression with assignment, indicators for site (randomization strata), and initial culture results as covariates.

Visual Function Questionnaire (VFQ). VFQ will be compared between arms controlling for Day 1 VFQ. NEI-VFQ in the US and the Indian-VFQ (IND-VFQ) in India. This will be conducted using linear regression with baseline and treatment assignment variables.

Pain Scale. Pain is assessed at day 0, day 1, and day 3 using a 0-10 scale for patient self-assessment. Multiple linear regression models will be used to evaluate 3-day pain by treatment arm while correcting for baseline pain.

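### Baseline covariates are imputed only above 10% missing; at or below that level no method is given, so adjusted models would lose randomized participants with observed outcomes

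*Protocol*

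**What the plan says.** Protocol 9.3 commits to strict intention-to-treat: "All participants randomized will be analyzed according to their allocation". Protocol 5.4 repeats this for the main analysis: "all patients who are enrolled will be randomized and included in the primary analysis".

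Protocol 9.3 then deals with missing data in three steps.

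- Complete case is always reported: "We will always report the results of complete case analysis, although such results are known to be biased".
- Baseline covariates have a trigger: "In the event of missing baseline covariates among >10% of patients, we will use regression based multiple imputation". That imputation uses at least 100 replicates and only other baseline variables. Nothing is said about 10% or less.
- Outcomes have no trigger: "we will also report multiple-imputation based analysis for missing outcomes", or an equivalent likelihood method, for comparison with the complete-case result.

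SAP 6.3 (REAGIR) covers missing outcomes only, with sensitivity analyses if more than 15% are missing. It has no rule for a missing baseline value, although its own models need many of them: "Baseline characteristics used in the censoring model will include treatment arm, site, age, sex, occupation, medication use at enrollment, eye trauma", followed by several ocular measures.

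Other models also adjust for baseline. The Protocol 9.4.1 primary model includes "indicators for study site (randomization strata), and BSCVA measured on Day 1 (before treatment"), while the SAP 6.2 primary model uses baseline pinhole acuity. The SAP's Cox model is for perforation "or the need for TPK while correcting for baseline infiltrate depth". The scar, VFQ and pain models each adjust for their own baseline value.

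**The concern.** Standard software drops a participant from a fitted model when any covariate in it is missing. With no method stated at 10% or less, and complete case the only default named, that is what would happen. The participant was randomized, may have completed follow-up and may have a measured outcome, yet would not contribute.

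Two things are at stake. The number analyzed would differ from model to model and fall short of all those randomized, despite the statements in Protocol 9.3 and 5.4. Outcome data already collected would also be discarded for want of a value whose only job is to improve precision. In a randomized comparison with a linear model, filling a baseline covariate without looking at arm or outcome does not bias the treatment contrast, so nothing is gained by the deletion.

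**Working it through.** **Inputs**

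- SD of BSCVA 0.293 and baseline correlation 0.216 (Protocol 9.2, SAP 3.3).
- REAGIR: 165 per arm, two-sided alpha 0.05, 15% loss, 90% power for 0.11 logMAR, 80% power for 0.10.
- SCUT II: 93 per arm, alpha 0.025, 15% loss, 80% power for 0.14 (Protocol 9.2).
- Trigger: more than 10% of patients (Protocol 9.3).
- Assumption: a share m of patients lacks a covariate in the model, independently of outcome loss. The documents give no value, so m runs over 2%, 5% and 10%, the last being the ceiling the rule allows.

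**Step 1: reproduce the plan's figures.** Residual SD = 0.293 × √(1 − 0.216²) = 0.286.

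REAGIR evaluable per arm = 165 × 0.85 = 140.25. Noncentrality = 0.11 / (0.286 × √(2/140.25)) = 3.22, which gives t-test power 0.894 against the stated 0.90.

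SCUT II evaluable per arm = 93 × 0.85 = 79.05, which gives 0.791 against the stated 0.80. Both are close enough to serve as the base.

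**Step 2: how many the rule could leave out.** In REAGIR, 10% of 330 = 33 patients can lack a covariate without triggering imputation. Those with an observed outcome number 330 × 0.85 × 0.10 = 28. In SCUT II, 10% of 279 = 27.9, so 27 patients, and 279 × 0.85 × 0.10 = 24 with outcomes.

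**Step 3: effect on the acuity model.** Multiply the evaluable n by (1 − m) and recompute t-test power.

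| m (assumed) | REAGIR patients with outcome left out | REAGIR power, 0.11 | REAGIR power, 0.10 | SCUT II patients with outcome left out | SCUT II power, 0.14 |
|---|---|---|---|---|---|
| 0 | 0 | 0.894 | 0.831 | 0 | 0.791 |
| 2% | 6 | 0.888 | 0.823 | 5 | 0.782 |
| 5% | 14 | 0.878 | 0.811 | 12 | 0.768 |
| 10% | 28 | 0.861 | 0.790 | 24 | 0.743 |

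**Step 4: a measure for the other linear models.** No planning SD or effect is given for VFQ, scar or pain. The standard error grows by 1/√(1 − m): about 1% at m = 2%, 3% at 5% and 5% at 10% (1/√0.90 = 1.054).

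**Step 5: which models are exposed.** Protocol 8.1 places every listed assessment except the VFQ in screening.

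- Day 1 VFQ: not a screening assessment, and scheduled at Visit 2 (Protocol 1.3). Exposed.
- Day 1 BSCVA: scheduled at Visit 2, whereas only pinhole acuity is scheduled at Day 0. Any model using it is exposed, including the primary model as Protocol 9.4.1 writes it.
- REAGIR pinhole acuity, slit-lamp findings, AS-OCT, Pentacam and confocal: scheduled at Day 0, and corneal thickness on AS-OCT is an eligibility item. Infiltrate depth and baseline images should rarely be missing.
- SAP 6.3 censoring and outcome models: about ten baseline variables at once, including occupation and symptom duration, so they depend on the most fields. They run only if more than 15% of outcomes are missing.

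**The case against.** **Deletion is not written down.** This is correct: it follows from silence at 10% or less combined with a complete-case default. The multiple imputation for missing outcomes has no threshold and proposes chained equations, which could also fill covariates. The text does not say it will, and that analysis is offered as a comparison to the complete-case result, so the gap stays open.

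**The data will mostly be there.** This largely stands. Screening collects most of the covariates, and Protocol 10.1.7 and 10.1.8 add full chart review, weekly data checks and site queries. It does not cover Day 1 VFQ or Day 1 BSCVA in the same way.

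**The power figures belong to the acuity model.** This also stands. REAGIR's SAP version of that model adjusts only for arm, site and pinhole acuity, so the 10% row is a bound for it and not a forecast.

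**Two stronger readings do not hold.** A reader might apply the 10% to each covariate separately and compound it: ten covariates each 3% missing independently would leave out 1 − 0.97¹⁰ = 26% with no single one above 10%. But the trigger counts patients with missing baseline covariates, so on its natural reading 26% would set imputation off. If the same patients lacked all ten, the loss would be 3%.

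A reader might also infer that the treatment estimate is biased or that intention-to-treat is broken outright. Participants stay in their allocated arm, the missing value predates treatment, and nothing in the documents shows missingness differing by arm in a way related to outcome.

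**The other SAPs may settle it.** Protocol 9.4.1 refers to separate plans for SCUT II and REAGIR II. They are not among the documents, so their handling is unknown.

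**Conclusion.** The concern holds as a minor one. Protocol 9.3 sets a threshold below which no method is given, SAP 6.3 does not fill the gap, and the likely result is that covariate-adjusted models leave out randomized participants with observed outcomes.

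What is shown is a modest loss of precision and an inconsistency with the stated analysis population. At the ceiling the rule permits, power in the REAGIR acuity model would drop by 3 to 4 percentage points, in SCUT II by about 5, and standard errors in any linear model would rise by about 5%. At 2% missing the REAGIR loss is under 1 point. These sizes assume that missing covariates are independent of missing outcomes and that software deletes incomplete records. The true share is not stated and is likely well below the ceiling for everything measured at screening.

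**What to change.** Delete the 10% threshold in Protocol 9.3 and state one rule for every covariate-adjusted model: a missing baseline covariate is imputed at any level of missingness, from baseline data only, without using arm or outcome.

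- Continuous covariates: one baseline-based value, such as the site mean or median.
- Categorical covariates such as occupation or eye trauma, where a mean has no meaning: a separate missing category or the multiple imputation already planned.

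Add the same rule to SAP 6.3 and say that it also covers the censoring and outcome models there. Check that the SCUT II and REAGIR II plans carry it. Complete-case results can still be reported alongside.

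The cost is a short paragraph in each document and slightly more analysis work, best settled before unmasking. A single fixed imputation is the simpler choice: the data are filled once and the 10,000 permutations run on that file. With at least 100 imputations, the same inference would need 100 × 10,000 = 1,000,000 fits and a stated way to combine them. In the Cox model, arm-blind filling may shift the hazard ratio slightly, but infiltrate depth should rarely be missing.
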